## 9.4. Safety Analyses

The Data Monitoring Committee (DMC) will review all safety data, including adverse events, after inclusion of 20%, 50% and 70% of patients. After each meeting, the DMC will make a recommendation of either continuation or discontinuation of the study to the steering committee. The DMC may also comment on the safety and overall conduct of the study. The responsibility

of continuing or discontinuing the study lies with the steering committee. The DMC charter will contain the details of the responsibilities of the DMC.

# 9.5. Interim Analyses

The DMC will perform an interim analysis of effect after half of the patients (n=253) have completed the first 28 days of follow-up and data on mortality are available for all these patients. The efficacy analysis will be performed on the primary outcome with a significance level of  $\alpha$ =0.0052 (see Section 9.2). If the analysis demonstrates an effect of the intervention, the study will be stopped early. Details will be presented in the DMC charter.

# 9.6. Data Monitoring Committee (DMC)

A Data Monitoring Committee (DMC), consisting of a leader (clinician), a statistician, and at least one more participant, will meet after inclusion of 20%, 50% and 70% of patients to assess the safety and overall conduct of the study. The members of the DMC will be independent of the study group and not otherwise involved in the study. A DMC charter will detail the responsibilities of the DMC, to be made available before the first DMC meeting.

## **10.** Supporting Documentation and Operational Considerations

## 10.1. Appendix 1: Regulatory, Ethical, and Study Oversight Considerations

#### 10.1.1. Regulatory and Ethical Considerations

- This study will be conducted in accordance with the protocol and with the following:
  - Consensus ethical principles derived from international guidelines including the Declaration of Helsinki
  - Applicable ICH Good Clinical Practice (GCP) Guidelines
  - Applicable laws and regulations
- The protocol, protocol amendments, ICF, documents describing the quality of the convalescent plasma product and other relevant documents (e.g., advertisements) will be submitted to the Regional Ethical Committee (REC) by the investigator and reviewed and approved by REC before the study is initiated.
- Any amendments to the protocol will require REC approval before implementation of changes made to the study design, except for changes necessary to eliminate an immediate hazard to study participants.
- Protocols and any substantial amendments to the protocol will require REC approval prior to initiation except for changes necessary to eliminate an immediate hazard to study participants.
- The investigator will be responsible for the following:
  - Providing written summaries of the status of the study to REC in accordance with the requirements, policies, and procedures established by REC.
  - Notifying REC of SAEs or other significant safety findings as required by REC procedures
  - Providing oversight of the conduct of the study at the site and adherence to requirements of ICH guidelines, the REC and all other applicable local regulations

## **10.1.2.** Informed Consent Process

- The principal investigator or a delegated contact person at the care home will explain the nature of the study to the participant or their guardian and answer all questions regarding the study.
- Participants must be informed that their participation is voluntary. Participants or their guardian will be required to sign a statement of informed consent that meets the requirements of REC and ICH guidelines.
- The study medical record must include a statement that written informed consent was obtained before the participant was enrolled in the study and the date the written consent

was obtained. The person obtaining the informed consent (e.g. investigator or delegated person) must also sign the ICF.

• A copy of the ICF must be provided to the participant or their guardian.

The ICF will contain a separate section that addresses the use of remaining mandatory samples for optional exploratory research. The investigator or delegated person will explain to each participant the objectives of the exploratory research. Participants will be told that they are free to refuse to participate and may withdraw their consent at any time and for any reason during the storage period.

A separate informed consent form (REK135924) will be required to document a participant's agreement to allow any remaining specimens to be used for exploratory research.

## 10.1.3. Data Protection

- Participants will be assigned a unique identifier by the sponsor. Any participant records or datasets that are transferred to the sponsor will contain the identifier only; participant names or any information which would make the participant identifiable will not be transferred.
- The participant must be informed that his/her personal study-related data will be used by the sponsor in accordance with Norwegian data protection law. The level of disclosure must also be explained to the participant who will be required to give consent for their data to be used as described in the informed consent
- The participant must be informed that his/her medical records may be examined by Clinical Quality Assurance auditors or other authorized personnel appointed by the sponsor, by appropriate REC members, and by inspectors from regulatory authorities.

## 10.1.4. Committees Structure

## **Data Monitoring Committee**

- Participant safety will be continuously monitored by the Sponsors designated Data Monitoring Committee (DMC).
- In addition, an early aggregated safety data review will be performed, the goal of which is to allow for a cautious, stepwise approach to [intervention] administration. An initial safety review for this study is planned for the first 50 participants/ 20 % of participants who are dosed and have provided safety data for 14 days after administration of convalescent plasma.
- All safety data collected will be summarized and reviewed by the DMC for agreement of next steps.
- In particular, data will be reviewed by the Sponsor for identification of the following events that would potentially contribute to a requirement to stop or pause the study.
  - Any deaths, regardless of causality
  - Any SAE
  - Any AESI (see table in Appendix 4)

- If a pausing rule is met, a decision will be made, based on the review, as to whether enrollment in the study will be allowed to resume.
- Safety data will also be included in the Norwegian Health Directorate's system for Hemovigilance monitoring (https://www.helsedirektoratet.no/rapporter/overvaking-av-blod-i-norge)

## 10.1.5. Dissemination of Clinical Study Data

Submission of results of the clinical study will be accelerated to the extent possible to inform the guidance on use of convalescent plasma in Norway. This will include but is not limited to description of primary and secondary study endpoints. Access to these data will be allowed for third parties following an independent assessment of the scientific merit of a rigorously defined research question. If the outcome is negative or the study is terminated, this will also be reported to the REC.

## 10.1.6. Data Quality Assurance

- All participant data relating to the study will be recorded on printed or electronic CRF unless transmitted to the sponsor or designee electronically (e.g., laboratory data). The investigator is responsible for verifying that data entries are accurate and correct by physically or electronically signing the CRF.
- Guidance on completion of CRFs will be provided in a specific SOP or Study Manual.
- The investigator must permit study-related monitoring, audits, | review, and regulatory agency inspections and provide direct access to source data documents.
- Monitoring details describing strategy, methods, responsibilities and requirements, including handling of noncompliance issues and monitoring techniques (central, remote, or on-site monitoring) are provided in the Monitoring Plan.
- The sponsor or designee is responsible for the data management of this study including quality checking of the data.
- The sponsor assumes accountability for actions delegated to other individuals (e.g., Contract Research Organizations).
- Records and documents, including signed ICFs, pertaining to the conduct of this study must be retained by the investigator for 5 years after study completion unless local regulations or institutional policies require a longer retention period. No records may be destroyed during the retention period without the written approval of the sponsor. No records may be transferred to another location or party without written notification to the sponsor.

## 10.1.7. Source Documents

- Source documents provide evidence for the existence of the participant and substantiate the integrity of the data collected. Source documents are filed at the investigator's site.
- Data reported on the CRF or entered in the eCRF that are transcribed from source documents must be consistent with the source documents or the discrepancies must be

explained. The investigator may need to request previous medical records or transfer records, depending on the study. Also, current medical records must be available.

- Definition of what constitutes source data:
  - o Data from Recruitment, Screening and Informed consent process
  - o CRF
  - Data on participant samples
  - o Databases collating the information collected during the study process
  - Analysis process documents and end reports
- The principal investigator must maintain accurate documentation (source data) that supports the information entered in the CRF.
- Study monitors will perform ongoing source data verification to confirm that data entered into the CRF by authorized site personnel are accurate, complete, and verifiable from source documents; that the safety and rights of participants are being protected; and that the study is being conducted in accordance with the currently approved protocol and any other study agreements, ICH GCP, and all applicable regulatory requirements.

#### 10.1.8. Study and Site Start and Closure

#### **First Act of Recruitment**

The study start date is the date on which the clinical study will be open for recruitment of participants.

The first act of recruitment is the first site open and will be the study start date.

#### **Study/Site Termination**

The sponsor or designee reserves the right to close the study site or terminate the study at any time for any reason at the sole discretion of the sponsor. Study sites will be closed upon study completion. A study site is considered closed when all required documents and study supplies have been collected and a study-site closure visit has been performed.

The investigator may initiate study-site closure at any time, provided there is reasonable cause and sufficient notice is given in advance of the intended termination.

Reasons for the early closure of a study site by the sponsor or investigator may include but are not limited to:

For study termination:

• Discontinuation of further study intervention development

For site termination:

• Failure of the investigator to comply with the protocol, the requirements of the REK or local health authorities, the sponsor's procedures, or GCP guidelines

- Inadequate or no recruitment (evaluated after a reasonable amount of time) of participants by the investigator
- Total number of participants included earlier than expected

If the study is prematurely terminated or suspended, the sponsor shall promptly inform the investigators, the REC, the regulatory authorities, and any contract research organization(s) used in the study of the reason for termination or suspension, as specified by the applicable regulatory requirements. The investigator shall promptly inform the participant and should assure appropriate participant therapy and/or follow-up.

## **10.1.9. Publication Policy**

- The results of this study may be published or presented at scientific meetings. If this is foreseen, the investigator agrees to submit all manuscripts or abstracts to the sponsor before submission. This allows the sponsor to provide comments.
- The sponsor will comply with the requirements for publication of study results. In accordance with standard editorial and ethical practice, the sponsor will generally support publication of multicenter studies only in their entirety and not as individual site data. In this case, a coordinating investigator will be designated by mutual agreement.
- Authorship will be determined by mutual agreement and in line with International Committee of Medical Journal Editors authorship requirements.

# 10.2. Appendix 2: Clinical Laboratory Tests

The tests detailed in this table are the recommended panel of routine testing to be offered in nursing homes. These are only required at the request of the doctor in charge at the care home (NOKLUS).

	Laboratory test	Response time	Distribution
Basic tests	Hemoglobin, CRP	Few hours	All care homes
	Glucose	<0.5 hours	All care homes
	Thrombocytes, Leukocytes with differential count (shipped to external laboratory)	2-3 days	All care homes
Extended repertoire	stended repertoire INR, fecal blood test		Some care homes
	Creatinin, sodium, potassium, calcium, thrombocytes, leukocytes with differential count, D- dimer (in-house laboratory)	2-3 hours	Few care homes

- These tests are of relevance for
  - Study inclusion/exclusion
  - Monitoring of study endpoints
  - AE monitoring
- Additional tests may be performed at any time during the study as determined necessary by the investigator or required by local regulations.

Investigators must document their review of each laboratory safety report.

# 10.3. Appendix 3: AEs and SAEs: Definitions and Procedures for Recording, Evaluating, Follow-up, and Reporting

#### **10.3.1. Definition of AE**

#### **AE Definition**

- An AE is any untoward medical occurrence in a clinical study participant, temporally associated with the use of study intervention, whether or not considered related to the study intervention.
- NOTE: An AE can therefore be any unfavorable and unintended sign (including an abnormal laboratory finding), symptom, or disease (new or exacerbated) temporally associated with the use of study intervention.

#### **Events Meeting the AE Definition**

- Any abnormal laboratory test results (haematology, clinical chemistry, or urine analysis) or other safety assessments (e.g., ECG, radiological scans, vital signs measurements), including those that worsen from baseline, considered clinically significant in the medical and scientific judgment of the investigator (i.e., not related to progression of underlying disease).
- Exacerbation of a chronic or intermittent pre-existing condition including either an increase in frequency and/or intensity of the condition.
- New conditions detected or diagnosed after study intervention administration even though it may have been present before the start of the study.
- Signs, symptoms, or the clinical sequelae of a suspected intervention- intervention interaction.
- The signs, symptoms, and/or clinical sequelae resulting from lack of efficacy will be reported as AE or SAE if they fulfil the definition of an AE or SAE.

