# **3. Objectives and Endpoints**

Objectives	Endpoints
Primary	
Assess the effect of convalescent plasma on mortality in COVID-19	Primary endpoint: All-cause mortality within the first 28 days of observation. Secondary endpoints: All-cause mortality within 60 days of observation.
Secondary	
Effect of convalescent plasma on recovery time in patients with active COVID-19 infection	Time from intervention to negative SARS-CoV-2 PCR during a 28 day observation period
Effect of convalescent plasma on clinical progression of COVID-19 disease	Requirement of oxygen therapy at days 1, 3, 7, 14, 21 and 28 compared to baseline Change in NEWS score at days 1, 3, 7, 14, 21 and 28 compared to baseline
Exploratory	
Effect of convalescent plasma on biomarkers in COVID-19	Change in CRP and lymphocyte count at day 1, 3, 7 and 14 in the study period. Time to normalized CRP and lymphocyte count
Safety of convalescent plasma in COVID-19	Incidence of adverse events

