# 8.3.5. Disease-Related Events and/or Disease-Related Outcomes Not Qualifying as AEs or SAEs

The following disease-related events (DREs) are common in participants with COVID-19 and can be serious/life threatening:

- Fever and/or chills
- Need for increased oxygenation or ventilation support
- Persistent pain or pressure in the chest
- New-onset confusion
- Multiple organ dysfunction or failure

Because these events are typically associated with the disease under study, they will not be reported according to the standard process for expedited reporting of SAEs even though the event may meet the definition of an SAE. These DREs will be followed by the medical monitor and recorded by the site designee for later evaluation by the Data Monitoring Committee (DMC).

NOTE: However, if either of the following conditions applies, then the event must be recorded and reported as an AE/SAE (instead of a DRE):

The event is, in the investigator's opinion, of greater intensity, frequency, or duration than expected for the individual participant.

OR

The investigator considers that there is a reasonable possibility that the event was related to study intervention.

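### Section 8.3.5 and Appendix 3 give competing rules for COVID-19 worsening, and AE status is partly tied to receiving plasma, so AE incidence can be ascertained unequally between arms

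*Protocol*

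**What the plan says.** Section 8.3.5 lists fever or chills, greater need for oxygen or ventilatory support, chest pain or pressure, new confusion and organ failure as disease-related events. Its heading reads "Disease-Related Events and/or Disease-Related Outcomes Not Qualifying as AEs or SAEs". Its body is narrower: these events "will not be reported according to the standard process for expedited reporting of SAEs even though the event may meet the definition of an SAE". They are followed by the medical monitor and recorded for the data monitoring committee (DMC).

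Two conditions, either of which suffices, move an event out of this class. One is that it is "of greater intensity, frequency, or duration than expected for the individual participant". The other is that the investigator thinks "there is a reasonable possibility that the event was related to study intervention". If either applies, "then the event must be recorded and reported as an AE/SAE (instead of a DRE"), so the two labels exclude each other.

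Appendix 3 (10.3.1, events meeting the AE definition) says that "clinical sequelae resulting from lack of efficacy will be reported as AE or SAE", on condition that they fulfil the AE or SAE definition. It does not mention disease-related events.

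The AE definition in 10.3.1 requires a temporal association with use of the study intervention, whether or not a causal relation is suspected. Section 8.3.1 collects SAEs from the start of intervention to day 60. The Schedule of Activities identifies the study intervention as the plasma transfusion. Section 6.2 states that the trial is open-label. The safety endpoint in Section 3, listed as exploratory, is "Incidence of adverse events".

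**The concern.** For a COVID-19 treatment, lack of efficacy shows itself as COVID-19 worsening. A plasma patient whose oxygen need rises therefore falls under both rules: a DRE under Section 8.3.5, and an AE or SAE under Appendix 3. A control patient with the same course cannot have a sequela of lack of efficacy, nor an event related to an intervention not given. Staff know the allocation when they choose the label, and the label decides whether the event enters the AE count.

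The full title promises safety compared with standard care. An excess of AEs on plasma could then partly reflect classification. The same data feed the DMC safety reviews at 20%, 50% and 70% inclusion, and Section 10.1.4 lists any SAE among the events that could contribute to a pause or stop.

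**Working it through.** **Do the two rules conflict?** The condition in Appendix 3 (that the definition be met) does not separate them. Section 8.3.5 concedes that a DRE may meet the SAE definition, and the AE definition covers new or exacerbated disease regardless of cause. Appendix 3 is also uneven within itself. Its first bullet leaves out laboratory and other safety findings that reflect progression of the underlying disease, while its last bullet brings lack of efficacy in. Neither section refers to the other.

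**Which routes to AE status are open in each arm?**

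| Route | Source | Plasma | Control |
|---|---|---|---|
| Worse than expected for the participant | 8.3.5 | yes | yes |
| Possibly related to study intervention | 8.3.5 | yes | no |
| Sequela of lack of efficacy | 10.3.1 | yes | no |

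**Where is the clock anchored?** The AE definition (10.3.1) and the start of SAE collection (8.3.1) both refer to the intervention, which the Schedule of Activities equates with transfusion. No equivalent start is given for controls.

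**How large could the effect be?** The protocol gives no AE or DRE rate, so no figure of its own can be reproduced. The following is an illustration on assumptions.

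- n = 253 per arm, from 506 patients (Section 9.2) randomised 1:1 (Section 9.3.1).
- p = true DRE risk, set equal in both arms.
- r1 = share of DREs relabelled as AEs in both arms by the worse-than-expected route.
- r2 = extra share relabelled on plasma only.

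AE incidence arising from DREs is p × r1 on control and p × (r1 + r2) on plasma. The ratio is (r1 + r2)/r1, whatever p is. The chance of a two-sided p < 0.05 uses the usual normal approximation for two proportions.

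With p = 30% and r1 = 20%, control incidence is 0.30 × 0.20 = 6%:

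| r2 | Plasma incidence | Ratio | Chance of p < 0.05 |
|---|---|---|---|
| 0 | 0.30 × 0.20 = 6% | 1.0 | 5% |
| 10% | 0.30 × 0.30 = 9% | 1.5 | about 25% |
| 20% | 0.30 × 0.40 = 12% | 2.0 | about 66% |
| 80% (every plasma DRE counted) | 0.30 × 1.00 = 30% | 5.0 | about 100% |

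Over p of 20% to 50%, r1 of 10% to 30% and r2 of 10% to 20%:

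- The ratio runs from (0.30 + 0.10)/0.30 = 1.33 to (0.10 + 0.20)/0.10 = 3.0.
- The difference p × r2 runs from 0.20 × 0.10 = 2 to 0.50 × 0.20 = 10 percentage points.
- The chance of a spurious p < 0.05 runs from about 14% to about 97%.

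These figures cover only AEs that arise from DREs. AEs of other kinds occurring equally in both arms would pull the overall ratio towards 1.

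**The case against.** The strongest case against is that Section 8.3.5 is the specific rule, written for COVID-19 with its own exceptions, while Appendix 3 is a general list. Reading the specific rule as governing is natural, and sites that do so will not use the lack-of-efficacy route. That is a fair reading, but the protocol does not state it. The relatedness route and the intervention-anchored definitions would remain in any case.

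Four stronger readings are tempting, and the protocol does not support them:

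- A reader might infer that every route back to AE status is confined to plasma. The worse-than-expected condition mentions no intervention and applies in both arms.
- A reader might infer that DREs escape safety reporting altogether. Only the heading suggests this. The body lifts expedited SAE reporting and keeps the events on record for the DMC, so a combined comparison by arm may still be possible.
- A reader might infer that real harm would be hidden. Under Section 8.3.5 alone, events that are possibly related or worse than expected must still be reported as AEs or SAEs, and Section 10.1.4 adds review of all deaths regardless of cause.
- A reader might size the problem by the 121 deaths in Section 9.2. Death is not on the DRE list. It is an SAE criterion, and mortality comes from the death registry in both arms.

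It can also be said that tabulation belongs in the SAP or the DMC charter, neither of which is shown. That holds for table layout. It does not hold for the definitions, because sites classify events at entry under the protocol and a later document cannot tell them which rule they should have followed.

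**Conclusion.** The point holds as an inconsistency with a plausible route to bias. Two rules apply to the same deterioration without a stated order, the heading of Section 8.3.5 is wider than its body, two of three routes to AE status presuppose plasma, and the AE definition and SAE window are anchored to an intervention that controls do not receive. With open-label classification, AE incidence can differ between arms without any true difference.

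A flat statement that AE incidence is not comparable would go too far. The supported conclusion is that ascertainment can be unequal, by an unknown amount. The ratios of 1.33 to 3.0 rest wholly on assumed rates and fall to 1.0 if the plasma-dependent routes are not used. Nor do the documents say that AEs go unrecorded in controls: the Schedule of Activities lists AE and SAE review without restricting it to one arm.

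The endpoint concerned is exploratory. The primary mortality analysis is unaffected.

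**What to change.** 1. Reconcile Section 8.3.5, heading and body, with the lack-of-efficacy sentence in Appendix 3, so that a single stated rule governs COVID-19 worsening in both arms.
2. Define AE and SAE collection from a time point common to both arms, for example randomisation, and word the AE definition so that it applies to controls.
3. For between-arm safety comparisons, including the DMC tables, count DREs, AEs and SAEs together by randomised arm, whichever route they were reported by.

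The cost is wording changes and one extra table, largely of events the protocol already has recorded. The combined count is less specific to effects of plasma, so transfusion reactions (Appendix 4) should still be shown separately.
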